# 2.2 Objectives

- 1. To develop and pilot test a check-up programme for adolescents that screens for important health conditions using accurate and acceptable screening tests and provides locally-accessible effective interventions (**Phase 1**)
- 1a To develop and pilot test a Digital Health and Well-being Club for adolescents as a basis for longer-term contacts with the adolescents (**Phase 1**)
- 2. Through a prospective intervention study in selected schools and communities in Chitungwiza, Zimbabawe to (**Phase 2**):
  - i. Evaluate the **implementation of the programme** by measuring key implementation outcomes: acceptability, adoption, appropriateness, feasibility, fidelity, and cost.

- ii. Describe the programme **context** and **mechanisms of action**.
- iii. Estimate **short-term programme impact on adolescent outcomes**: health-related knowledge; intentions, agency, and perceived social support for behaviour change; engagement with health services; health-related behaviours; well-being, improvements in previously-diagnosed health and well-being conditions.
- iv. Estimate the **cost-effectiveness** of the programme in reducing overall disease burden and improving adolescent well-being
- v. **Obtain information on key parameters needed for the planning of a next phase larger evaluation study**: prevalence of health conditions and behaviours, acceptability of referral, feasibility of following-up programme participants, initial estimates of the impact of the programme on longer-term health, educational and well-being outcomes, and optimal implementation of the Y-Check intervention.
- 3. To refine the programme and its theory of change, and finalise optimal methods for the measurement of impact of the programme in future studies (**Phase 3**).

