In this hybrid effectiveness-implementation study, both data on implementation process, and adolescent outcomes will be captured. A mixed-methods process evaluation will describe the programme implementation, context, and mechanisms of action. The study cohort will be followed up for approximately 12 months with adolescent process and outcome data collected at screening, 4-month and 12-month follow-up visits (**Figure 2**). An economic evaluation will estimate unit costs per adolescent screened, condition identified and case treated, and estimate the cost-effectiveness of the intervention in improving adolescent well-being. Where data are available, we will estimate the impact

of the intervention on DALYs averted. We will gather information to develop methodologies for a potential larger future study to measure the longer-term health, well-being and educational impact of the programme. We will assess the scale up and financial sustainability of the programme.

The prospective intervention study design is more appropriate than a randomised controlled trial (RCT) for answering the research question because i) it is impossible to measure the adolescent outcomes in the absence of the screening which is an integral part of the Y-Check intervention; ii) the intervention components are known to be effective for identifying conditions for which known effective interventions exist (e.g. Provision of spectacles for adolescents with myopia; provision of psychological interventions by trained lay mental health providers through the "Friendship Bench" approach for adolescents with symptoms of significant common mental health disorders), so a control arm in which adolescents were screened, found to have these conditions but not offered care would be unethical; and iii) the great majority of conditions being screened for are chronic, so the prevalence of previously undiagnosed and untreated conditions or risky behaviours provides its own counterfactual reflecting a lack of prior appropriate diagnosis and effective treatment.

COVID-19, which the WHO declared a pandemic on 11 March 2020, has had significant effects on research activities worldwide. Over the past 18 months, adaptations to procedures have allowed research activities to continue in a safe environment for research staff and participants.

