# 6. Statistical considerations and Data analysis

## **6.1 Outcomes**

Outcomes (see Section 4.3.2) will be assessed using:

- Programme data collected during the check-up visit and at the referral services
- Research data collected through the pre-consultation questionnaire, exit interview, and during follow-up visits in the subsequent 12 months.
- School register data for the 12 months before and after Y-Check school visits

The primary outcome will be the proportion of those screening positive for at least one condition who receive appropriate on-the-spot care or complete appropriate referral for all identified conditions within 4 months.

- Completed referral is defined as attending at least the first referral appointment. We expect referral/treatment to have occurred within 4 months.
- Where a client has been diagnosed with more than one condition they must have had completed
  care or referral for each of those conditions in order to be included in the numerator for the
  primary outcome.

Secondary implementation outcomes:

- The proportion of those who screen positive for individual conditions that have had their condition correctly managed within 4 months
- Yield of previously undiagnosed and un-referred conditions
- Intervention acceptability, adoption, appropriateness, feasibility, fidelity and cost (see Process Evaluation Section 4.3.3 for further details)

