## **Prospective Intervention study**

We will follow the STROBE guidelines for the reporting of cohort studies. We will create a flowchart showing the number of communities and schools and the number of participants per community and school at each contact point in the cohort study. We will use descriptive analysis to compare the community-level and school-level characteristics of the four study communities and schools.

The primary outcome is a single proportion which will be presented with a 95% confidence interval for each of the 4 target populations: 10-13y male, 10-13y female, 16-19y male, 16-19y female. Secondary outcomes which are measured at a single time point will be presented in a similar way. For outcomes which are measured at two or more time-points, a before-after analysis will be conducted comparing differences in measures between the two time-points. The unit of analysis will be the individual. For clinical outcomes which are measured at two or more time-points, the initial check-up visit (baseline) will give the prevalence of undiagnosed and untreated chronic conditions which will represent the counterfactual. The proportion of undiagnosed and untreated chronic conditions at the 4-month follow-up visit will be formally compared to this counterfactual to estimate the effectiveness of the intervention in improving these clinical outcomes. We will assess health service and client determinants of correct management of conditions at 4 months using multivariable regression.

**Digital platform data** De-identified data on information viewed, games played, rewards provided/used along with programmatic data on behaviours and clinical conditions etc. will be analysed using machine learning approaches to understand the sub-groups/segments of adolescents who participate in Y-Check. This analysis will help us to define, develop, and pilot test targeted messaging for different sub-groups of young people who attend Y-Check follow-up visits. We will also analyse this data to develop algorithms which could potentially be used in the future phases of the Y-Check programme to further personalise the Y-Check user experience to maximise relevance, uptake and retention.

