If the adolescent is diagnosed with a condition that is considered to be less serious and/or less seriously stigmatized, the trusted adult (Y-Check 2 community hub) or the parent/guardian (Y-Check 1 and Y-Check 2 school-recruited) will be sent a letter indicating the diagnosis and the recommended treatment/action. Trusted adults or parents/guardians will be encouraged to support their adolescent through their treatment/care. The letter will also offer a way for the adult/parent to get an appointment with their adolescent so that they can ask any questions and receive advice/support as needed. If the adolescent needs their adult to accompany them to a referral appointment, then the Y-Check team would attempt to contact the adult by telephone or through a home visit. Otherwise, there will be no follow-up if the adult/parent does not take up the offer of an appointment.

If the adolescent is generally well then the adolescent will receive a one-page summary telling them what has been checked for and that nothing serious has been found. They will be encouraged to continue good health-related behaviours. They will be told about health and well-being services available at the school, the health facility and in the community. For Y-Check 1 and Y-Check 2 (school-recruited), the letter will be sent from the school to the parents. For Y-Check 2 (community-hub), the adolescent will receive the letter and will be encouraged to share with their trusted adult(s).

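### Section 6.3 reads the fall in undiagnosed and untreated conditions as clinical effectiveness, but the check-up changes that status by design, so the measure falls substantially even if no condition improves

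*Protocol*

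**What the plan says.** Protocol section 6.3 (Prospective Intervention study) gives clinical outcomes measured repeatedly their own rule. First, "the initial check-up visit (baseline) will give the prevalence of undiagnosed and untreated chronic conditions which will represent the counterfactual". Then: "The proportion of undiagnosed and untreated chronic conditions at the 4-month follow-up visit will be formally compared to this counterfactual". The stated purpose is "to estimate the effectiveness of the intervention in improving these clinical outcomes".

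Section 2.3 relies on the same idea when it explains why there is no control arm: because most of the conditions are chronic, "the prevalence of previously undiagnosed and untreated conditions or risky behaviours provides its own counterfactual reflecting a lack of prior appropriate diagnosis and effective treatment".

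Other parts of the Protocol bear on what this measure can show:

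- Section 3.7.3 (Station 5) has the nurse review all results at the visit and treat or refer.
- Section 3.7.2 and Appendix 1 have iron and folic acid supplied at the visit to participants found anaemic.
- Section 6.1 uses the word 'diagnosed' for a client whose referrals may still be outstanding: "Where a client has been diagnosed with more than one condition they must have had completed" care or referral for each one.
- Section 7.6 provides that, for less serious conditions, the parent or trusted adult "will be sent a letter indicating the diagnosis and the recommended treatment/action".
- Objective 2.iii (section 2.2) asks about "improvements in previously-diagnosed health and well-being conditions".
- Appendix 1 lists the secondary clinical outcomes mostly as status, severity or level: anaemia, visual impairment, hearing impairment, severity of symptoms, blood pressure.

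**The concern.** The quantity compared at 4 months combines two things: whether a condition is present, and whether it has been picked up or treated. The intervention acts on the second directly and at once. A participant leaves the count on being diagnosed or on being treated, whatever has happened to their sight, haemoglobin or symptoms. Someone anaemic at baseline who was given supplements and is still anaemic at 4 months is no longer untreated, and so drops out.

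The comparison therefore shows mainly that screening and linkage to care took place. Section 6.3 reports it as clinical improvement. It also excludes by construction the diagnosed conditions that objective 2.iii asks about. If the sentence is followed as written, an intervention that improved nobody's condition could be reported with a large and highly significant clinical benefit. Because section 2.3 uses the same counterfactual to justify the uncontrolled design, the reading carries weight beyond a single table.

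**Working it through.** The Protocol gives no effect size, power or interval for this comparison, so there is no stated figure to reproduce. The check is to count what the section 6.3 measure would show if no condition improved at all.

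**Inputs from section 6.2**
- 50 of 1000 participants in one age group screen positive for a condition, so D = 50 and the baseline is 5.0%.
- Referral completion is 75% in one example and 50% in the other.

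**Assumptions, not in the Protocol**
- All 50 are true cases, undiagnosed and untreated before the visit.
- No improvement, no new cases, full follow-up.
- Screening sensitivity s from 1.0 down to 0.7, with independent errors at the two visits.

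**Two readings of 'diagnosed'**, with d the fraction of detected cases that leave the count:
- A: told positive at the check-up, d = 1.
- B: only once the referral visit is attended, d = 0.75 or 0.50, with no on-the-spot treatment.

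**Formula.** True cases number D/s, so D/s − D are missed at baseline. At 4 months the measure counts missed cases now detected, (D/s − D)·s = D(1 − s), plus detected cases that did not leave the count and test positive again, D(1 − d)·s. The sum is D(1 − d·s).

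| Reading | s | Count at 4 months | Measure at 4 months | Apparent fall |
|---|---|---|---|---|
| A, d = 1 | 1.0 | 50 × (1 − 1.0) = 0 | 0% | 100% |
| A, d = 1 | 0.9 | 50 × (1 − 0.9) = 5 | 0.5% | 90% |
| A, d = 1 | 0.8 | 50 × (1 − 0.8) = 10 | 1.0% | 80% |
| A, d = 1 | 0.7 | 50 × (1 − 0.7) = 15 | 1.5% | 70% |
| B, d = 0.75 | 1.0 | 50 × (1 − 0.75) = 12.5 | 1.25% | 75% |
| B, d = 0.75 | 0.7 | 50 × (1 − 0.525) = 23.75 | 2.4% | 53% |
| B, d = 0.50 | 1.0 | 50 × (1 − 0.50) = 25 | 2.5% | 50% |
| B, d = 0.50 | 0.7 | 50 × (1 − 0.35) = 32.5 | 3.25% | 35% |

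**Significance in two of these cases.** At s = 1.0 all changes go one way, so the exact McNemar p-value for n one-way changes is 2 × 0.5ⁿ. Reading A, n = 50: 1.8 × 10⁻¹⁵. Reading B with 50% completion, n = 25: 6 × 10⁻⁸. The first is the extreme case.

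**Status-based measure under the same assumptions.** Screen-positives at 4 months number (D/s)·s = 50, so the result is 5.0% against 5.0%. It shows no effect, which is correct here.

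**The case against.** The strongest reply is that section 6.3 does not stand alone. The same paragraph plans a general before-after analysis of every outcome measured repeatedly. Section 6.1 includes the Appendix 1 clinical outcomes among the client outcomes, and Figure 1 has screening repeated at 4 and 12 months. A status comparison is thus largely provided for, and the defect is one sentence at odds with the Protocol's own outcome list. That stands: a reader might infer that this is the plan's only formal effectiveness comparison, and the text does not support that. It does not rescue the sentence, which is the specific rule for clinical outcomes and the one said to estimate effectiveness in improving them.

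A reader might also infer that the check-up diagnoses every positive, so that the measure must drop to about zero. The Protocol does not support this either. Section 3.7.2 sends epilepsy positives elsewhere for diagnosis, treats hypertension as only suspected, and refers vision and hearing failures for further examination. Sections 6.1 and 7.6 use 'diagnosed' more loosely, so usage is mixed. That is why both readings are worked through. About zero occurs only under reading A with near-perfect sensitivity and no new cases.

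Finally, a reader might infer that the DALY estimates inherit the error. No section says they are built on this comparison. Section 4.3.4 makes them conditional on data being available, and the modelling paragraph in 6.3 refers to the effectiveness of condition-specific interventions.

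The primary outcome is a separate single proportion and is not affected.

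**Conclusion.** The point holds in this form: the 4-month quantity in section 6.3 mixes care status with clinical status, and its fall cannot be read as clinical improvement. With zero improvement in the section 6.2 example, the measure falls by 70–100% if being told at the check-up counts as diagnosis, and by 35–75% if diagnosis waits for the referral visit. The true change is nil. These sizes rest on the stated assumptions about sensitivity, follow-up and new cases; new cases would make the apparent fall smaller. The direction does not depend on which reading of 'diagnosed' is taken. The mismatch with Appendix 1 and objective 2.iii follows from the text alone and needs no assumption.

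**What to change.** Replace the section 6.3 sentence with wording such as: *For each Appendix 1 clinical outcome measured at both visits, the outcome as listed there (condition status, severity or level on the same test and cut-off), regardless of diagnosis or treatment status, will be compared between baseline and 4 months among participants measured at both visits.*

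- Outcomes that are uptake or care measures (ART adherence, immunisation, circumcision) are analysed as listed. A rule based on whether the condition is still present would not suit them: HIV infection, for example, persists under successful care.
- Report the fall in undiagnosed and untreated conditions separately, as a process result on yield and coverage.
- Align the counterfactual wording in section 2.3.
- Use all participants measured at both visits. Restricting to baseline positives would build in regression to the mean.

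The cost is one sentence in 6.3 and matching wording in 2.3. Where screening is repeated as Figure 1 plans, no further data are needed. Section 4.3.2 allows fewer tests at follow-up, so the comparison is limited to outcomes whose test is repeated. The reported effect will be less favourable than under the present wording.

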## 7. Ethical Considerations

# 7.1 Collaborative partnerships

Community representatives will be involved in the design of the intervention and will engage with the research team to shape the intervention. Participatory co-design will be conducted with several stakeholders including adolescents, family members of adolescents, health care providers in schools and at health facilities, including those involved in clinical care, and counselling / outreach, CHWs, representatives or key informants from CBOs that are engaged in providing adolescent health services and community members and other gatekeepers. The formative research completed in 2020 is described in a separate protocol that was approved by local and international ethics committees (Protocol numbers as follows- MRCZ: MRCZ/A/2560; WHO Ethics Review Committee (ERC.0003284); London School of Hygiene & Tropical Medicine LSHTM/A/18058).

The research teams will continue to actively engage with the study communities at various levels (for example with government structures, healthcare facilities at management and worker level, existing NGOs and CBOs providing community-based services and other stakeholder groups). As discussed in Section 4.2, a YAG will be established and will provide guidance and feedback to the study team.

#### 7.2 Social value

Adolescents have relatively poor access to promotive, preventative and curative healthcare. If this study is able to show that the intervention is effective and cost-effective, it could contribute to meeting the Universal Health Coverage goals along with SDG 3. In addition, the inclusion of HIV-testing and referral for treatment will contribute to achievement of the UNAIDS goals which have been laid out as a means to ending the HIV epidemic. The multifaceted approach of the intervention offers value to adolescents in the community even if the intervention does not impact immediately on clinical or educational outcomes.

#### 7.3 Scientific validity

Adolescents stand out as a group that have not benefitted from the numerous interventions to reduce the burden of communicable and non-communicable diseases and studies have consistently shown that this age-group are less likely to access health services especially when they have no symptoms of illness. This study will determine if providing check-up visits at two time-points during adolescence improves the detection of undiagnosed and untreated conditions and in doing so improves health and well-being. Furthermore, the study addresses the broader issue of access to services by adolescents. It is well-recognised that adolescents face substantial barriers to accessing health services in facilities and health services in many countries give low priority to this age-group which has contributed to their poorer health gains compared with young children or adults over recent decades. Therefore if school and community-based provision of services does result in high uptake (particularly of sensitive services

such as SRH and HIV services), this may provide a model for delivery of other health services to adolescents.

The study will be conducted according to the most rigorous standards of research and will provide an understanding about the process of implementing the intervention as well as the impact of such an intervention. Study procedures, the analysis, interpretation and dissemination of findings, and the formulation of policy and programmatic recommendations will be guided by local and international experts in adolescent health (see **Section 9 Collaborators and Scientific Advisors**). The study results will be shared throughout the study with national and international policy-makers to ensure that the findings are understood and that lessons from the study are implemented.

#### 7.4 Risk-benefit assessment

The risks and benefits of the Y-Check intervention will be described to participants and their parents/guardians during the consent process. Y-Check participants will benefit from early detection of health problems, health promotion, and the development of health-seeking behaviours. Those who choose to participate can opt out of responding to questions or completing examinations/procedures. HIV and STIs are conditions, which are associated with stigma and anxiety. The Y-Check team will provide counselling to those participants testing positive for HIV or STIs. There is also a risk of negative consequences of a parent or guardian finding out that an adolescent has a drug or alcohol problem. However, if needed, participants and their parents or guardian will have access to on-the-spot initial Y-Check counselling services and assisted referral to longer-term services. The protocols and procedures for communicating with adolescents and their families will be carefully developed in collaboration with the YAG and community stakeholders.

As for any health care, the tests and treatment provided can have side-effects that can be serious or minor. The tests could cause anxiety. The blood test could cause discomfort or a small bruise, as with any other blood test. While the possibility of this happening is low, the informed consent and assent forms will specify these risks clearly to make sure that participants are aware of the possibility. In the unlikely case of an adverse event, the team will be trained to provide care and support, as well as notify the relevant school authorities (for those seen in schools). If urgent care is required, they will be supported to attend a local health facility.

Risks will be minimized by explaining the procedures in detail to adolescents during the school sessions, as well as during the process of obtaining informed consent in schools and community venues. Staff will be trained to detect adverse events and a protocol will be in place to ensure action in the rare case that such an event occurs.

The use of a digital questionnaire is convenient and has the advantage of providing anonymity; however, adolescents may have fears over unauthorised access and trust. There is also a risk to participants of a breach of confidentiality and possible rejection and discrimination by friends and family if they test positive for any of these conditions. The study team will put in place procedures to mitigate these fears. The Y-Check team will be trained in good clinical practice, data protection and confidentiality, and counselling for participants testing positive for any previously mentioned conditions. Adolescents who have low literacy or low digital literacy skills may find completing the tablet self-screening challenging, and the option of a face-to-face interview will be available.

